3.3.7. Recovery and Time to Recovery

A Secondary Endpoint measure requires the time to recovery assessed through Study Visit Day 29. Recovery will be defined as having a value of 1, 2, or 3 on the 8-point ordinal Clinical Status score. The time to recovery will be defined as the elapsed time (in days) from randomization to the earliest day at which a subject reaches recovery. Note that since clinical status assessments are recorded as defined in Section 4.3, the day that is being assessed (not necessarily the day the response is collected) will be used to determine the timing of events. For example, a subject with a score of 5 recorded on study days 1-3 and a score of 3 recorded on study day 4 will have a time to recovery equal to 3 days. It is also possible that a subject has a clinical status ordinal score > 3 reported for a particular day but was subsequently discharged on the same day. If a subject is discharged to a location other than hospice or another hospital the subject will be considered recovered at the time of discharge but may be reviewed by the Endpoint Review Committee, if other data suggests the subject may not be recovered (e.g., the subject is re-admitted). If a subject is discharged to hospice or another hospital, re-admitted, or is a special case where recovery handling may be unclear, the subject's data will be reviewed by the Endpoint Review Committee to make the determination of whether the subject should be considered recovered and, if so, at what time point in the analyses. Subject data to be reviewed as part of this determination will include the reported clinical status scores while hospitalized, where the subject was discharged to (e.g. private residence, rehabilitation facility, long-term care/nursing home, comfort and care), and any information regarding readmittance. Additional information may be solicited to assess recovery.

Any subjects that are lost to follow-up or terminated early prior to an observed recovery will be censored at the day of their last observed assessment. Subjects who complete follow-up but do not experience recovery will be censored at the day of their Study Visit Day 29. All deaths that occur on or before Study Visit Day 29 (and prior to any observed recovery) will be considered censored at Day 29. Note that we do not expect many subjects to worsen after discharge. However, we will evaluate whether any discharged subjects subsequently experience a worse clinical status and sensitivity analyses will be conducted accordingly. For these analyses, subjects who recover but are later re-admitted for COVID-19 will not be considered a recovery but will instead be censored at 28 days.

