3.3.2. Study Day and Time to Event

Use of "Day 29" or "Day 15" are references to actual study days and represent 28 and 14 days post-randomization, respectively. References to visits such as "Study Visit Day 29" and "Study Visit Day 15" pertain to protocol-defined visits which may occur on any day within the defined visit window and not necessarily on Day 29 and Day 15.

Time-to-event endpoints are based on actual study days, e.g., Day 29 or Day 15. Endpoints that are not specifically defined as a time-to-event are based on Study Visits, irrespective of the study day upon which the visit was conducted. As a result, time-to-event endpoints at Day 15 and Day 29 may not match corresponding Clinical Status Ordinal Scores at Study Visit Day 15 and Study Visit Day 29. For example, all subjects with Clinical Status in Category 7 or 8 recorded for Study Visit Day 29 performed on or after Day 31 may not count as events by Day 29 unless there is additional corroborating data (e.g., Death or Supplemental Oxygen Case Report Forms).

3.3.3. Mechanical Ventilation-Free Survival at Day 29

Subjects who do not report an ordinal score in Category 8 (Death) or Category 7 (hospitalized on invasive mechanical ventilation or ECMO) at any point following randomization up to and including Day 29 will be

considered to have survived free from mechanical ventilation. The proportion of subjects who survive through Day 29 free from mechanical ventilation will be estimated using a Kaplan-Meier method, allowing definition of time-to-event and time-to-censoring for all subjects.

The time-to mechanical ventilation or death is defined as the elapsed time in days from randomization to the earliest day at which the subject requires mechanical ventilation or dies. The day the subject requires mechanical ventilation is defined as the first day reporting an ordinal score in Category 7. Note (as in Section 3.3.4), this should be the date the subject is assessed, and not the date the score is reported. The time-to-event for subjects discharged to hospice or other end-of-life care prior to Day 29, but for whom a death date is unknown and with Day 60 data unavailable, will be the number of days from randomization to discharge.

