8.1.2.4. Time to Recovery

In the mITT population, the time to recovery, as defined in Section 3.3, will be analyzed using a stratified log rank test to compare treatment to control through Day 29. Stratification is based on actual baseline Status ordinal score (ordinal score 5, ordinal score 6). As noted in Section 3.3, all deaths within 29 days will be considered censored at Day 29 with respect to time to recovery. Conceptually, a death corresponds to an

infinite time to recovery, but censoring at any time greater than or equal to Day 29 gives the same answer as censoring at Day 29; both correspond to giving deaths the worst rank.

The treatment hazard ratio estimate and confidence interval and p-value from the stratified log rank test will be presented ([Table 28](#)). The median time to event and 95% confidence intervals will be summarized by treatment group and actual baseline Clinical Status ordinal score. Kaplan-Meier curves will also be generated by treatment arm ([Figure 15](#), [Figure 16](#), [Figure 17](#)).

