Repeat for the As Treated Population.

N= Number of subjects in the specified treatment group, actual baseline ordinal score, and analysis population.
n = Number of recovered subjects.
Difference is the difference in the restricted mean recovery time between PBO + Dexamethasone + RDV to Baricitinib + PBO + RDV.
^a Tau is the truncation time point for the Restricted Mean Survival Time analysis and is equal to the minimum of the largest observed times in each group

Programming Notes:

Within an actual baseline ordinal score stratum:

```
proc lifetest data=enrevent plots=(rmst) method=breslow rmst(cl);
by stratum;
time evntday * Censor(1);
strata trtcode /diff=all;
ods output rmst=rmst;
run;
```

Stratified by actual Baseline Ordinal Score (“Baseline Ordinal Score 5 or 6” row).

```
proc lifetest data=enrevent plots=(rmst) method=breslow rmst(cl);
time evntday * Censor(1);
strata trtcode CRSEVERE /diff=all;
ods output rmst=rmst;
run;
```

Table 35: Summary of Recoveries and Deaths by Day 29 – mITT Population

Grouping Variable	Actual Baseline Ordinal Score	Treatment Group	Recovered ^b		Did Not Recover		Deaths ^b		Died or Not Recovered		
			n	%	n	%	n	%	n	%	
Actual Baseline Ordinal Score	5	Baricitinib + PBO + RDV (N=X)	x	x	x	x	x	x	x	x	
		PBO + Dexamethasone + RDV (N=X)	x	x	x	x	x	x	x	x	
	6	Baricitinib + PBO + RDV (N=X)	x	x	x	x	x	x	x	x	
		PBO + Dexamethasone + RDV (N=X)	x	x	x	x	x	x	x	x	
	Baseline Ordinal Score 5 or 6	Baricitinib + PBO + RDV (N=X)	x	x	x	x	x	x	x	x	
		PBO + Dexamethasone + RDV (N=X)	x	x	x	x	x	x	x	x	
	Any Baseline Ordinal Score ^a	Baricitinib + PBO + RDV (N=X)	x	x	x	x	x	x	x	x	
		PBO + Dexamethasone + RDV (N=X)	x	x	x	x	x	x	x	x	
Repeat for duration of symptoms categories in Section 6.4											
N= Number of subjects in the mITT Population.											
^a [X] additional subjects are included in the ‘Any Baseline Ordinal Score’ row that were enrolled with a baseline ordinal score of 4. [Include as applicable]											
^b [Number] subjects recovered but subsequently died. These X subjects are included in both the recoveries and also in the deaths counts.											

Programming Note: For the categories of “Recovered”, “Did Not Recover” and “Deaths”, subjects who recover but subsequently die will be classified under “Recovered” and “Deaths”. If there are cases of this, footnote b will be added.

Table 36: Time to One or Two Category Improvement on the 8-Point Ordinal Scale by Treatment Group, Actual Baseline Ordinal Score 5 or 6

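### Time to recovery has two unreconciled horizons, actual Day 29 and Study Visit Day 29; the worst-rank argument for deaths holds only under the first, and Table 34's RMST horizon can drift past 28 days

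*SAP*

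**What the plan says.** SAP 3.3.7 opens with the visit as its horizon: "A Secondary Endpoint measure requires the time to recovery assessed through Study Visit Day 29". It censors unrecovered survivors by the same clock: "Subjects who complete follow-up but do not experience recovery will be censored at the day of their Study Visit Day 29". Deaths follow a different clock: "All deaths that occur on or before Study Visit Day 29 (and prior to any observed recovery) will be considered censored at Day 29". Section 3.3.8 repeats this pair of rules for time to improvement.

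Section 3.3.2 separates the two terms. References to Day 29 "are references to actual study days and represent 28 and 14 days post-randomization, respectively", whereas study visits "pertain to protocol-defined visits which may occur on any day within the defined visit window and not necessarily on Day 29 and Day 15". Its own example is a "Study Visit Day 29 performed on or after Day 31".

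Other sections use actual Day 29. Section 3.2 counts recovery only up to and including Day 29, 3.3.2 bases time-to-event endpoints on actual study days, and 8.1.2.4 runs the stratified log-rank test through Day 29. Section 8.1.2.4 then defends the handling of deaths by saying that "censoring at any time greater than or equal to Day 29 gives the same answer as censoring at Day 29", so that either choice ranks deaths worst.

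The RMST footnote to Table 34 (Appendix 1) defines the truncation time tau, which "is equal to the minimum of the largest observed times in each group".

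**The concern.** Censoring deaths at Day 29 is equivalent to censoring them at any later time only if no recovery is counted after Day 29. Section 3.3.7, taken alone, leaves room for such recoveries: survivors are followed to a visit that may come after Day 29, by which time every death has left the risk set. Late recoveries would then be compared among survivors only, and an arm with fewer deaths would lose part of its advantage.

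The section that derives the variable and the section that analyses it therefore support different programs for a test in the fixed sequence of 6.8. The adjacent rule for time to death (3.3.6) avoids the problem by censoring completers at the earlier of the visit and actual Day 29. Sections 3.3.7 and 3.3.8 have no such line.

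The RMST analysis has a related problem. A survivor's censoring time at a late visit is an observed time, so it can set tau even if no late recovery counts as an event.

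**Working it through.** The plan gives no figure to reproduce here. The check is of a logical statement, followed by its likely size. The SAP gives neither the visit window nor a late-recovery rate, so the rates below are assumptions.

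**1. Does the equivalence hold if late recoveries count?** Take four subjects per arm. Each arm has one recovery at 30 elapsed days. Arm 1 also has three unrecovered survivors, and arm 0 has three deaths.
- Deaths censored at 28 days: 5 at risk, 4 of them in arm 1, and 2 events. E = 2 × 4/5 = 1.6. O − E = 1 − 1.6 = −0.6. V = 2 × 0.8 × 0.2 × 3/4 = 0.24. Z = −0.6/√0.24 = −1.22.
- Deaths kept at risk: 8 at risk, 4 in arm 1. E = 1, O − E = 0, Z = 0.00.

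The two choices differ, so the statement in 8.1.2.4 fails under this reading.

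**2. Trial-sized data.** Unstratified log-rank test with 691 per arm (1382/2, from Table 1). Assumed: 5% alive and unrecovered, deaths as shown, and the same proportion of late recoveries in each arm at 29 to 31 elapsed days.

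| Late recoveries | Deaths | Z, literal 3.3.7 | Z, deaths kept at risk | Gap | Z, all truncated at 28 days |
|---|---|---|---|---|---|
| 0% | 5% vs 8% | 1.411 | 1.411 | 0 | 1.411 |
| 0.5% | 5% vs 8% | 1.385 | 1.407 | 0.022 | 1.389 |
| 1% | 5% vs 8% | 1.369 | 1.419 | 0.050 | 1.378 |
| 1% | 5% vs 12% | 3.156 | 3.261 | 0.105 | 3.176 |
| 3% | 5% vs 8% | 1.293 | 1.427 | 0.134 | 1.315 |
| 3% | 5% vs 12% | 3.011 | 3.294 | 0.283 | 3.063 |

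With equal mortality (5% vs 5%) every version gives Z = 0 in this symmetric set-up. With events truncated at 28 days, censoring deaths at 28 or later gives identical Z in every scenario, so 8.1.2.4 is then correct. The literal and truncated versions differ by at most 3.063 − 3.011 = 0.052, but late recoveries were set equal in the two arms.

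**3. Hand check.** Assume 750 per arm, 12% alive and unrecovered at Day 29, deaths 4% vs 8%, and 13 late recoveries per arm. The low-mortality arm's share of the late risk set is 12/24 without deaths and (12 + 4)/(24 + 12) = 16/36 with them. The shift in O − E is 26 × (12/24 − 16/36) = 1.44. With V about 270 to 300, that is 0.08 to 0.09 in z, against the arm with fewer deaths.

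**4. RMST.** While the curve is flat, each day of horizon beyond 28 adds the unrecovered share to an arm's mean. On the assumptions of step 3 the shares are 0.12 + 0.04 = 0.16 and 0.12 + 0.08 = 0.20. Five extra days (assumed) add 0.8 and 1.0 day to the two means. The between-arm difference moves by 5 × 0.04 = 0.2 day.

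**The case against.** The strongest reply is that the horizon is fixed elsewhere. The endpoint definition in 3.2, the general rule in 3.3.2 and the analysis in 8.1.2.4 all limit recovery to actual Day 29. On that reading a recovery on Day 30 or later is not an event, survivors' later censoring times change nothing in the log-rank test, and deaths do receive the worst rank. This stands. A reader might infer from 3.3.7 that the plan simply fails to rank deaths worst. The documents do not support that, because the failure depends on which horizon is programmed.

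The size is also open to challenge. Thirteen late recoveries per arm is about 14% of the 90 unrecovered survivors assumed (13/90), within a few days. The test is reached only if four earlier hypotheses are rejected. Both points stand.

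On RMST, tau is a minimum across arms, so both arms in a row share one horizon and the contrast within a row is valid. The analysis is exploratory, and Table 34 has a column that shows tau. A reader might take the 0.8 to 1.0 day added to each arm's mean as a change in the treatment effect. It is not, since most of it cancels in the difference.

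The contradiction between sections remains. Section 8.1.2.4 sends the reader to 3.3 for the definition, and 6.5 does the same for endpoint-specific censoring, so a programmer following 3.3.7 is following the plan.

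**Conclusion.** The point holds as an unreconciled horizon: Study Visit Day 29 in 3.3.7 and 3.3.8 against actual Day 29 in 3.2, 3.3.2 and 8.1.2.4. The loss of worst rank is conditional on late recoveries being counted. In that case the gap between the two ways of censoring deaths is about 0.02 to 0.28 in z for late recoveries of 0.5% to 3% and unequal mortality. It is zero with no late recoveries.

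The RMST point does not depend on counting late recoveries. If each arm in a row has an unrecovered survivor whose visit came after Day 29, tau exceeds 28 days in a table titled by Day 29, and it can differ between the score 5, score 6, pooled and As Treated rows. The effect on a between-arm difference is about 0.2 day under the assumed five days and 0.04 difference in unrecovered share.

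The consequences are small, but the horizon of a test in the hierarchy should be unambiguous. Time to improvement has the same wording but lies outside the hierarchy.

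**What to change.** - **3.3.7 and 3.3.8:** count only recoveries or improvements on or before actual Day 29. Censor event-free completers at the earlier of Study Visit Day 29 and actual Day 29, as 3.3.6 does for death, and censor deaths without the event at 28 days. Change the opening sentence of 3.3.7 to refer to actual Day 29.
- **Table 34:** set tau to 28 days for every row, in the footnote and in both code blocks.

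Section 8.1.2.4 can then stay as it is, because its statement becomes true. The cost is a sentence or two in each subsection, one footnote and one code option. No new data are needed and the sample size is unaffected.

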8.2.5. Additional Analyses of Time-to-Recovery

The analysis of Time-to-Recovery will be repeated in the mITT population but including only subjects with actual baseline Clinical Status scores in ordinal score 5 or 6 (excluding those with any other baseline score) and in the As-Treated population. The analysis will also be repeated using the Modified Recovery ordinal scale described in Section [4.3](#) ([Table 29](#)).

Sensitivity analyses will be performed using Cox proportional hazards models to estimate the hazard ratio ([Table 29](#)). First, a mITT analysis will be performed in which subjects who die prior to recovering are treated as experiencing a competing risk in the Fine-Gray proportional hazards regression model. Second, a Cox

model will be fit with binary indicators for treatment group and baseline ordinal score (5 or 6) as well as a treatment * baseline ordinal score (as a continuous variable) interaction terms. The models will be fit to the mITT analysis population. The treatment group hazard ratios and CIs will be reported for both sets of models and the interaction term p-value will be reported for the interaction models. The tabular summary will also include results from an analysis of time to recovery controlling for age and duration of symptoms as continuous covariates and baseline d-dimer and CRP values as continuous covariates.

The time-to-recovery analysis will also be repeated using the other subgroups defined in Section 6.4 in place of actual baseline ordinal score. Each subgroup will be considered separately, and the tabular and graphical summaries described in the previous section will be replicated for each subgroup. Forest plots (Figure 18 and Figure 19) will be generated to display the overall treatment hazard ratio estimate and CI from each of the within-subgroup analyses (Table 30).

As noted in Section 6.4, analyses that take into account concomitant medication will be performed (Table 32). An additional sensitivity analysis will evaluate the effect of recoveries that were not sustained as indicated in Section 3.3.2 (Table 31).

A restricted mean survival time analysis will be performed as an exploratory analysis. The restricted mean recovery time estimates will be provided for each treatment group and actual baseline ordinal score stratum as well as the difference in restricted mean recovery time between treatment groups within each of the baseline ordinal score strata (Table 34).

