Two corroborative summaries will also be generated. A summary of the number and percentage of subjects in each treatment group who recovered (and are alive), did not recover (and are alive), and died by Day 29 will be summarized. The summary will also include the numbers and percentages, grouping deaths and non-recoveries together (Table 35). The summaries will also be provided by the Modified Recovery ordinal scale (Table 33) and the duration of symptoms categorizations specified in Section 6.4.

Other censoring techniques and additional analyses of the primary outcome may be performed.

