The “Actual Baseline Ordinal Score” and “Analysis Population” columns will be removed. A “Subgroup” column will be inserted to the left of the “Treatment Group” column. This table will not display the “Any...” rows. The elements for the “n” and “Median Time to Recovery” columns will display “-“. This table will include subgroups (see Section 6.4), except for actual baseline ordinal score.

Programming Notes for Table 31 and Table 32:

P-values will not be included in these tables.

Table 31 will include a column to the left of the “n” column titled “m”. The corresponding footnote will read “m = Number of subjects readmitted for COVID-19.” Table will include the following footnote: “In this analysis, subjects that recover and are subsequently readmitted for COVID-19 are censored at 28 days”.

Table 32 will include a column to the left of the “n” column titled “m”. The corresponding footnote will read “m = Number of subjects reporting use of a medication of interest.” The “Analysis Population” column will be replaced by a column labeled “Medication of Interest”. Separate models will be fit with censoring based on the first date of use for each of the following categories of medications (see Section 6.4):

- Any Medication of Interest
- Antivirals
- COVID-19 Vaccination
- Treatments for COVID-19
- Monoclonal antibodies targeting the spike protein of SARS-CoV-2 including casirivimab, imdevimab, and bamlanivimab
- Renin-angiotensin system (RAS) Inhibitors and HMG-CoA reductase inhibitors (Statins)

- Corticosteroids
- Other Anti-Inflammatory Drugs

The table will include the following footnote: "In this analysis, subjects that reported use of the specified medications of interest are censored at time of medication receipt."

Table 34: Time to Recovery by Day 29 by Treatment Group and Actual Baseline Ordinal Score: Restricted Mean Survival Time Analysis, Actual Baseline Ordinal Score 5 or 6

Analysis Population	Treatment Group	Actual Baseline Ordinal Score	n	Tau ^a	Restricted Mean Recovery Time (Days)		Difference	
					Estimate	95% CI	Estimate	95% CI
mITT Population	Baricitinib + PBO + RDV (N=X)	5	x	x	x.x	x.x, x.x	x.xx	x.xx, x.xx
	PBO + Dexamethasone + RDV (N=X)		x	x	x.x	x.x, x.x		
	Baricitinib + PBO + RDV (N=X)	6	x	x	x.x	x.x, x.x	x.xx	x.xx, x.xx
	PBO + Dexamethasone + RDV (N=X)		x	x	x.x	x.x, x.x		
	Baricitinib + PBO + RDV (N=X)	Baseline Ordinal Score 5 or 6	x	x	x.x	x.x, x.x	x.xx	x.xx, x.xx
	PBO + Dexamethasone + RDV (N=X)		x	x	x.x	x.x, x.x		

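### The check on unsustained recovery covers COVID-19 readmission but not death, and Tables 20 and 35 count recovered-then-died subjects as Recovered although the text says alive

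*SAP*

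**What the plan says.** **Main definition.** SAP Section 3.3.7 measures time to recovery "from randomization to the earliest day at which a subject reaches recovery", with no requirement that recovery last. On deaths it states: "All deaths that occur on or before Study Visit Day 29 (and prior to any observed recovery) will be considered censored at Day 29". Section 8.1.2.4 refers back to Section 3.3 but describes the rule as covering every death within 29 days, and explains it as giving deaths the worst rank.

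**Check on durability.** Section 3.3.7 then announces that "we will evaluate whether any discharged subjects subsequently experience a worse clinical status and sensitivity analyses will be conducted accordingly". The rule that follows is "subjects who recover but are later re-admitted for COVID-19 will not be considered a recovery but will instead be censored at 28 days". Section 8.2.5 describes the same analysis more broadly: "An additional sensitivity analysis will evaluate the effect of recoveries that were not sustained as indicated in Section 3.3.2". (The rule is in Section 3.3.7, so that cross-reference is also wrong.) The planned Table 31 footnote reads: "In this analysis, subjects that recover and are subsequently readmitted for COVID-19 are censored at 28 days".

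**Summary tables.** For Table 35, Section 8.2.5 plans the number and percentage in each "treatment group who recovered (and are alive), did not recover (and are alive), and died by Day 29 will be summarized". Section 8.2.1 uses the same recovered-and-alive category for Table 20. The programming notes to both shells say that "subjects who recover but subsequently die will be classified under “Recovered” and “Deaths".

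**The concern.** Death is Category 8, the worst status on the scale, so it is the clearest case of a recovery that was not sustained. The operative rule in Section 3.3.7 and the Table 31 footnote is narrower than the aim stated in Section 3.3.7 and the description in Section 8.2.5, and it omits death. A durability analysis that keeps such subjects as recoveries cannot show whether the recovery result depends on them. Time to recovery is the fifth and last test in the hierarchy of Section 6.8.

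The second problem is one of execution. A programmer cannot satisfy both the text of Sections 8.2.1 and 8.2.5 and the shell notes, and the two give different Recovered counts whenever someone recovers and then dies.

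**Working it through.** The plan states no figure on this point, so the check is mainly a comparison of rules, followed by two illustrations of size.

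**1. Subjects who first recover and then die by Day 29**

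- *Readmitted for COVID-19, then dies.* Committee review is required because of the readmission. Table 31 removes the recovery.
- *Readmitted for another cause, then dies.* Committee review is required. If the recovery is not reversed, it stands in Table 31.
- *Discharged home or to a nursing home, dies without readmission.* Section 3.3.7 permits review but does not require it. The recovery stands in Table 31 unless reversed.
- *Reaches Category 3, dies in hospital before discharge.* No rule requires review unless the case is treated as unclear. The recovery stands in Table 31 unless reversed. This case lies outside the aim in Section 3.3.7, which speaks of discharged subjects, but inside the wording of Section 8.2.5.

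**2. Other planned recovery analyses**

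The Fine-Gray model in Section 8.2.5 treats as competing events only deaths before recovery. Table 53 tracks change from Day 29 to Day 60, so it does not address deaths by Day 29. Read literally, Section 8.1.2.4 would censor the last three cases at Day 29 even in the main analysis, whereas Section 3.3.7 keeps them as events. Its reasoning, that a death amounts to an infinite time to recovery, fits only deaths before recovery.

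**3. Overlap in Table 35**

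Let N be the subjects in an arm and k those who recover and then die by Day 29. The shell note puts the k subjects in Recovered and in Deaths, hence also in Died or Not Recovered. Then:

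Recovered + Died or Not Recovered = N + k, and the percentages sum to 100 × (N + k)/N.

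Take N = 750, which is the planned 1500 of Section 5 divided by two (equal allocation assumed). The SAP does not give k.

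- k = 1: 751/750 = 100.13%
- k = 5: 755/750 = 100.67%
- k = 10: 760/750 = 101.33%
- k = 20: 770/750 = 102.67%

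Under the section text the groups are exclusive and the sum is 100%.

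**4. Possible effect on the recovery hazard ratio**

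A simulation (40 replicates per k) assumed 750 per arm, exponential recovery times with 85% recovered by 28 days in both arms, and all k subjects in one arm. Those k were recoded from recovered to censored at 28 days. That arm's recovery hazard ratio against the other was multiplied on average by:

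- k = 5: 0.982
- k = 10: 0.966
- k = 20: 0.933

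The 85% rate and the values of k are assumptions. Placing all k in one arm is the extreme case.

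**The case against.** Several points on the other side stand.

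- **The Committee is a real safeguard.** Section 3.3.7 requires review of any readmission, whatever its cause, and of unclear cases, and a recovery can be reversed. A reader might infer that Table 31 is the only protection against unsustained recovery. It is not. But no rule requires review for death at home or in hospital after Category 3, and the shell notes presuppose that some recovered-then-died subjects stay recoveries.
- **The deaths are not hidden.** A reader might infer that the plan passes deaths off as successes. Each death by Day 29 is an event in the primary endpoint and in mortality, the fourth test, ahead of recovery. It is also the worst DOOR category at Day 29 and appears under Deaths in Tables 20 and 35.
- **The double count is disclosed.** Both shells plan a footnote with the number of subjects concerned. The footnote does not make the Recovered column match the text, and neither shell asks for the number by arm.
- **Not every post-recovery death escapes Table 31.** If 0.5% to 1.5% of 1500 subjects died after recovery (an assumption), that would be 7.5 to 22.5, or 8 to 23 subjects. This is the total, not the number Table 31 would miss, since deaths after a COVID-19 readmission are already removed and the Committee may reverse others.
- **The tables could be reconciled the other way,** by deleting the alive qualifier from the text. That ends the contradiction but leaves the groups overlapping.
- **Table 31 is a readmission analysis by title, reports no p-values and is supportive.** This limits the severity but does not bring its rule into line with Section 8.2.5.

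**Conclusion.** The point holds, with minor severity. The stated durability rule is narrower than its stated purpose: a subject who recovers and dies by Day 29 without a COVID-19 readmission remains a recovery in Table 31 unless the Committee reverses it. Section 8.1.2.4 states the death rule without the limit in Section 3.3.7. The text and shells for Tables 20 and 35 conflict. The illustrated excess over 100% for Recovered plus Died or Not Recovered applies to Table 35 only, because Table 20 has no Died or Not Recovered column.

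The number affected is unknown and probably small, since Section 3.3.7 expects few subjects to worsen after discharge. Under the assumptions above, ten such subjects all in one arm would move the recovery hazard ratio by about 3%. The primary analysis and control of type I error are not affected.

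**What to change.** - **Section 3.3.7 and the Table 31 footnote:** censor at 28 days any subject who, after first recovery, dies by Day 29 or is readmitted for COVID-19. Correct the cross-reference in Section 8.2.5 to Section 3.3.7.
- **Section 8.1.2.4:** limit the censoring of deaths to those before any observed recovery, as in Section 3.3.7.
- **Tables 20 and 35:** count as Recovered only subjects who recovered and are alive at Day 29, as Sections 8.2.1 and 8.2.5 say. Put recovered-then-died subjects under Deaths only, and give their number by arm in the footnote.

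The cost is a few lines of SAP text and a small programming change on data already collected. The main recovery definition stays as it is. The rule should be settled before unblinding so that it is not chosen after the results are known.
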